Alcohol withdrawal status. The Clinical Institute Withdrawal Assessment for Alcohol, revised version (CIWA-Ar) will be administered and scored at every visit. Using this scale mild alcohol withdrawal is defined with a score less than or equal to 15. For participants who score in the mild range, we will record the score and continue with the visit. For participants in the moderate (scores of 16 to 20) or severe (scores > 20) ranges, visits are discontinued and follow-up procedures are conducted, including notifying the responsible clinician ([name], Co-I). Visits that are discontinued do to moderate or severe CIWA-Ar scores will be rescheduled.

Description of neuropsychiatric study visit measures. The neuropsychiatric study visit battery was designed to assess a full range of neuropsychiatric symptoms (e.g., AUD severity, cravings, depression, anxiety, fatigue, pain) and cognitive skills (e.g., attention, memory, executive function). The cognitive domains were selected for assessment because previous research by our group and others has demonstrated that HCV is associated with impairments in these domains (Huckans et al., 2009, Huckans et al., 2011). The present study follows up on these findings by evaluating whether individuals who receive DAA therapy for HCV evidence improved psychiatric and cognitive function, and the extent to which AUDs impact outcomes. Measures were selected because of their sound psychometric properties (e.g., reliability, validity, large normative sample that can be corrected for demographics), and because they are widely used by clinicians and have established clinical utility. *The neuropsychological measures that will be repeated have equivalent versions that will be alternated across study visits to minimize practice effects.* Measures will be administered according to published standard administration procedures.

Psychiatric and substance use disorder diagnoses

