MRI Imaging Acquisition: We will use the Human Connectome Project (HCP) Lifespan Protocol using a 3T Siemens Magnetom Prisma scanner and a 32-channel phased array head coil. **fMRI (T₂^{*}-weighted):** Three (2 PDD and 1 DSNBACK) T₂^{*}- weighted echo-planar imaging (EPI) functional runs will be acquired (60 slices, 2 mm thick, TR/TE/α=2000 ms/38 ms/55°, matrix=128 × 128, FOV=220 mm², PAT mode/Accel factor = GRAPPA/2, 310 volumes per run) with an in-plane pixel size of 2.0 mm² while subjects perform the PDD or the DSNBACK. Each run will be 10.3 minutes long. **rsfMRI:** Identical to fMRI settings with 200 volumes. **High-resolution anatomical (T₁-weighted [T_{1w}]):** One magnetically prepared rapid acquisition gradient echo (MPRAGE) (208 0.8 mm isovoxels, TR/TE/TI/α = 2400 ms/2.24 ms/1060 ms/8°, FOV=256x240 mm, 2x Parallel Imaging, duration 6.38 min), will be acquired for co-registration with functional images and statistical overlay. **High-resolution anatomical (T₂-weighted [T_{2w}]):** 208 slices, 0.8 mm isovoxels, TR/TE: 3200 ms/564 ms; variable flip angle; FOV 256x263 mm, 2x Parallel imaging; Futsyion 5.57 min. **HARDI:** Two HARDI scans will be acquired (66 axial slices, 2.2 mm thick, TR/TE/α = 4300 ms/96 ms/90°, FOV= 25.6 cm², PAT mode /Accel factor = GRAPPA/2) consisting of six non-diffusion weighted (B₀) images followed by 32 non-collinear directions at B₀ = 1000 s mm⁻² and at B₀ = 2000 s mm⁻². Each HARDI scan lasts 4.73 min.

fMRI Standard Preprocessing: Task-related and resting-state fMRI data will be preprocessed identically. We include only scans with minimal movement (< 3 mm) and free of artifacts (Murphy et al., 2013). Functional images will be realigned for motion corrections, unwarped then co-registered to structural images for each subject and then transformed to Talairach coordinates and then resampled into atlas space with 3 mm isovoxels. Motion correction is applied with the standard 6 parameters and then frame-by frame spatial deviations are assessed with the temporal derivative of the time course.

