The anatomical volume is then segmented into gray matter, white matter, and cerebrospinal fluid. Next, we apply a temporal bandpass filter ($0.009 \text{ Hz} < \nu < 0.08 \text{ Hz}$), spatial smoothing (6 mm full width at half maximum (FWHM) Gaussian kernel), regression with the 6 rigid body motion parameters, regression of the whole brain signal and regression of the signal for ventricles and white matter. Opposite phase-encode polarity spin echo images will be used to estimate the B_0 distortion field, which will be applied to each gradient echo frame after accounting for estimated head motion. Gradient nonlinearity distortions will be corrected using scanner-specific field maps. Both corrections are vital for proper registration to structural images. Images will be preprocessed using AFNI_16.1.26. To enable cortical surface-based analyses, fMRI time courses will be sampled to the cortical surface mesh, using the extent of overlap with the cortical ribbon as a weighting factor to account for partial voluming. Voxels with high variability relative to their local neighborhood will be excluded. The functional EPI images will be despiked (3dDespike), slice time corrected (3dTshift), motion corrected (3dvolreg), aligned to warped MPRAGE (align_epi_anat.py) and corrected for oblique slice acquisition. A 4 mm FWHM three-dimensional Gaussian blur will be applied to the functional images (3dmerge) and each voxel time series will be scaled to have a mean of 100 (3dTstat, 3dcalc).

Anatomical (T_{1w} and T_{2w}). MPRAGE and T_{2w} structural images will be corrected for gradient nonlinearity distortions using scanner specific, nonlinear transformations, provided by MRI scanner manufacturers, and verified using phantom scans. Spatial distortion in the readout direction due to B_0 variation will be corrected based on the distortion maps generated from our fast field mapping. T_{2w} images will be registered to T_{1w} images using mutual information after coarse pre-alignment via within-modality registration to atlas brains. Intensity non-uniformity correction will be performed by dividing image intensities by a smooth bias field estimated from the geometric mean of the T_{1w} and T_{2w} images. Anatomical scans will be corrected for oblique acquisition, skull stripped (3dSkullStrip), and warped into MNI-152 space with @auto_tlrc.

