Neuroimaging measures. We will use the methods of the Fair Laboratory (Miranda-Dominguez et al., 2014) to analyze the rsMRI scans. We will use an ROI-to-ROI approach to calculate connectivity in the pre-processed data, based on the a priori regions previously associated with alcohol effects. Bivariate correlations between the average (BOLD) signal from these regions provide connectivity estimates. Several sources of spurious variance along with their temporal derivatives are then removed from the data through linear regression (e.g., signal from ventricular regions and signal from the white matter). The magnitude of connectivity changes between groups will be compared utilizing two-tailed t-tests. The raw p-values will be corrected for multiple comparisons and thresholded at a false discovery rate (FDR) correction of PFDR < 0.05 . Data from discounting tasks will be fit to equations using a softmax procedure (Miedl et al., 2012). We calculate the fractional areas under the discounting curves as impulsivity measures.

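### The between-group test of connectivity change has no group-level motion term and no stated check of motion by group, so residual head movement that differed by AUD would be neither adjusted for nor seen

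*Combined protocol and SAP*

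**What the plan says.** All references are to the combined protocol and SAP.

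- **Scan selection (fMRI Standard Preprocessing).** "We include only scans with minimal movement (< 3 mm) and free of artifacts". The section adds that "frame-by frame spatial deviations are assessed with the temporal derivative of the time course". It states no frame-wise threshold and no later use of that assessment.
- **Resolution.** Functional slices are acquired at 2 mm (MRI Imaging Acquisition) and "resampled into atlas space with 3 mm isovoxels".
- **Within-scan handling (same preprocessing section).** Images are realigned and unwarped. There is also "regression with the 6 rigid body motion parameters, regression of the whole brain signal and regression of the signal for ventricles and white matter", and despiking.
- **Further cleaning (Neuroimaging measures).** "Several sources of spurious variance along with their temporal derivatives are then removed from the data through linear regression". The examples given are ventricular and white-matter signal; motion is not named.
- **Group test (Neuroimaging measures).** "The magnitude of connectivity changes between groups will be compared utilizing two-tailed t-tests", with FDR correction at 0.05. No covariate is listed.
- **Other outcomes (Neuropsychiatric and laboratory measures).** A linear model in AUD, HCV and their interaction is used. Variables that may change over time, such as TLFB and CIWA-Ar scores, enter as differences. This rule is not extended to imaging.
- **Withdrawal at visits (Alcohol withdrawal status).** Mild means a CIWA-Ar score of 15 or less. "For participants who score in the mild range, we will record the score and continue with the visit".

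**The concern.** Regressing motion parameters out of each scan reduces the effect of movement on that scan. It does not guarantee that what remains is equal across people or groups. If the residue, or its change between visits, differs by AUD and is related to measured connectivity, an unadjusted t-test attributes part of it to AUD.

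Two features of the plan make such an imbalance plausible. Visits continue at CIWA-Ar scores up to 15, and Table 2 projects TLFB changes of -18 and -36 in the AUD+ groups against 0 and -1 in the AUD- groups. Neither is evidence about head movement.

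Connectivity bears on Hypotheses 1.2 and 2.2. Expected outcomes and alternative considerations counts improved functional connectivity as support and anticipates weaker benefit with AUD, so the AUD contrast is the one exposed. FDR correction takes the p-values as valid; it does not repair a biased contrast.

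**Working it through.** **1. The plan's own figures.** The Power section gives 80% power for a 0.51 SD main effect at the 0.05 level, with 30 per group (60 v 60). SE = √(2/60) = 0.183 SD. Power is 0.798 (normal) or 0.791 (noncentral t, 116 df). For the 0.91 SD interaction at the 0.10 level, SE = √(4/30) = 0.365 SD and power is 0.802 or 0.798. Both reproduce. The fmripower result cannot be checked because its error terms are not given. This point disputes none of these figures.

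**2. Inputs for the bias calculation.** The documents supply neither of the following, so both are assumptions:

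- dm: the AUD+ v AUD- difference in residual motion change, in SD;
- r: the within-group correlation of motion change with a connection's change.

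The section does not say which groups each t-test compares, so 60 v 60 (pooled over HCV) and 30 v 30 (two single groups) are both shown.

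**3. Formula.** With no true effect, the spurious difference is r × dm, in SD of connectivity change. The false-positive rate is the power of a two-sided 0.05 t-test at that difference, with SE = √(2/n).

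Worked case, r = 0.2 and dm = 0.5: the spurious difference is 0.2 × 0.5 = 0.10 SD.

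- 60 v 60: 0.10/0.183 = 0.55 standard errors, giving 8.4%.
- 30 v 30: SE = √(2/30) = 0.258, so 0.10/0.258 = 0.39 standard errors, giving 6.7%.

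| r | dm | Spurious difference (SD) | 60 v 60 | 30 v 30 |
|---|---|---|---|---|
| any | 0 | 0 | 5.0% | 5.0% |
| 0.1 | 0.3 | 0.03 | 5.3% | 5.1% |
| 0.2 | 0.5 | 0.10 | 8.4% | 6.7% |
| 0.3 | 0.5 | 0.15 | 12.9% | 8.8% |
| 0.3 | 0.8 | 0.24 | 25.6% | 15.0% |

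These are rates for one connection before FDR correction. No rate under the planned FDR rule is derived.

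**4. Effect of adjusting.** In simulations of 20,000 runs per case (r = 0.2 with dm = 0.5, and r = 0.3 with dm = 0.5 and 1.0, at both sample sizes), adding motion as a covariate returned the rate to 4.9-5.1%.

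**5. Cost in power.** Adjustment multiplies the SE by √(1 - r²) × √(1 + dm²/4). For r = 0.2 and dm = 0.5 this is 0.980 × 1.031 = 1.010, and power at 0.51 SD (60 v 60) is 0.78 against 0.79 unadjusted. Over r = 0.1 to 0.4, power is 0.77-0.84 at dm = 0.5 and 0.70-0.77 at dm = 1.0. Steps 4 and 5 use a two-group model; the factorial model was not simulated.

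**The case against.** The strongest reply is that the plan already does a good deal about motion: realignment, six-parameter and whole-brain regression, ventricle and white-matter regression, despiking, and a screen for artifacts as well as for movement. This stands. A reader might infer that motion is ignored; the text does not support that. The gap is only at group level and concerns a residue of unknown size.

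Second, nothing in the documents shows that movement differs by AUD. The CIWA-Ar rule sets a ceiling and does not say where participants score. If the contrast is pre-post change, a stable AUD difference in movement largely cancels, and bias needs a change in movement that differs by group. This also stands. If the contrast is cross-sectional, a stable difference would be enough; the wording leaves this open.

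Third, it is tempting to say that frame-wise motion is never used. The text says only that it is assessed and states nothing further; the cited methods may contain more. Nor do the documents support a claim that motion would shift many connections in one direction, particularly as whole-brain signal is regressed out.

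Fourth, connectivity is not a row in Table 2, whose footnote calls its entries the primary outcome variables. That limits the importance of the point but does not remove it.

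**Conclusion.** The plan states neither a group-level motion covariate nor a check of motion by group for the connectivity comparison, and adding both would improve it. This is a refinement. It does not correct a wrong figure or resolve a contradiction.

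The possible size runs from nothing (no imbalance, 5%) to 25.6% per connection at 60 v 60, or 15.0% at 30 v 30, at the upper end of the tabulated assumptions. The 8.4% and 6.7% figures are illustrations and not estimates for this study. A reader might infer that an AUD effect on connectivity would be a movement artefact, or that the 3 mm limit is unsound. The documents support neither: they give no movement data, and 3 mm, although larger than an acquired slice, equals one atlas voxel. What can be said is that the stated analysis could not tell a true AUD effect from imbalanced residual movement.

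**What to change.** In Neuroimaging measures:

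1. Summarise each participant's frame-wise motion at both visits from the realignment output. The plan does not say that such a per-person summary is produced, so it should be defined, but it needs no new data.
2. Replace the t-test with a linear model containing AUD, HCV, AUD × HCV and the post-minus-pre change in mean frame-wise motion, keeping the FDR correction. If a contrast is cross-sectional, use that visit's own motion value. State which contrast is meant. This extends the change-score covariate rule already used for the neuropsychiatric and laboratory outcomes.
3. Report motion by group and visit.
4. Show the unadjusted result beside the adjusted one.

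The cost is one degree of freedom, a few lines of text and some power if the imbalance is large. If motion is itself a disease effect, the model may over-adjust; the paired unadjusted result would let a reader see how much the conclusion depends on the adjustment. The 3 mm limit can stay, and no change to visit procedures is implied.

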If the Veteran chooses to complete the first study visit by telephone or video, Veterans will be mailed informed consent materials (VA Informed Consent form, OHSU Informed Consent form, and VA HIPAA Authorization) and first visit materials (questionnaires). After the Veteran receives the study materials, a trained study team member will call the Veteran to go through the informed consent procedures and answer any questions. If the Veteran chooses to participate, he or she will sign the VA Informed Consent form, OHSU Informed Consent form, and VA HIPAA Authorization, and mail them back to [name] using a pre-addressed and stamped envelope. Immediately after signing the consent forms, participants will have the option to complete portions of the neuropsychiatric study

visit measures, which includes the clinical interview, neuropsychiatric interview, neuropsychological assessment, and questionnaire battery via telephone or videoconference. Twelve of the fourteen neuropsychological assessments can be administered by phone or video. The remaining neuropsychological assessments will be administered at the time of the participant's next in-person visit. This research data will be collected from the participant prior to the study team receiving the signed informed consent forms and HIPAA authorization. Remaining research data and specimen collection will occur at the time of their next in-person research study visit once the signed informed consent forms and HIPAA authorization have been received.

Neuropsychiatric study visits. Clinical research staff will complete a standardized neuropsychiatric study visit protocol with eligible participants who provide informed consent. The protocol will be conducted twice for each participant (baseline and 12 weeks after DAA therapy completion).

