 - NAB Judgment - measure of everyday problem-solving/executive function
 - Categories – measure of mental flexibility and categorization
 - Word Generation – measure of initiation and mental flexibility.

Questionnaire battery. AUD Identification Test-C [AUDIT-C; 3-item screening tool to be administered at baseline only (Bush et al., 1998)]; Severity of Dependence Scale (SDS) (Gossop et al., 1997, Gossop et al., 1995); Alcohol Timeline Followback (TLFB) (to be administered in-person at pre- and post-DAA therapy study visits, as well as over the phone at weeks 12 and 18). In addition to in-person interviews, the TLFB has demonstrated reliability and validity over the phone (Sobell, 1992, Sobell et al., 1996); Clinical Institute Withdrawal Assessment for Alcohol scale, revised (CIWA-Ar) (Sullivan et al., 1989); Visual Analogue Scale (rates level of craving for alcohol over the past 24 hours on a scale of 0 to 100); Beck Depression Inventory, Second Edition (BDI) (Beck, 1996); Generalized Anxiety Disorder Inventory (GAD) (Argyropoulos et al., 2007) and PCL-C (Weathers et al., 1994); Fatigue Severity Scale (FSS) (Krupp et al., 1989); Brief Pain Inventory, Short Form (BPI) (Cleeland and Ryan, 1994), and Sickness Impact Profile (Bergner et al., 1981).

Specimen collection and laboratory measures. At study visits, oral fluid is collected and used toward HIV antibody screening by OraQuick (OraSure Technologies Inc.) or similar "in-home" oral swab test and alcohol testing by Alco-Screen (Chemetrics, Inc.) or similar alcohol saliva test. Urine is collected and used for urine alcohol [*i.e.*, ethyl glucuronide (EtG) levels] and drug analysis and pregnancy tests. EtG assessments are done with EtG Alcohol Test Dip Cards (Rapid Exams Inc.). Drug analysis and pregnancy tests are conducted using 5 panel Drug Screen Cups (Rapid Exams Inc.) and human chorionic gonadotropin (hCG) urine dip card tests (Rapid Exams Inc.), respectively. Blood is collected by a trained phlebotomist or trained VA research personnel in four, 8 mL capacity Cell Preparation Tubes (CPTs, BD Biosciences) for planned experiments (≤ 32 mL of blood is collected at both the initial and 6-month study visits). If not already obtained per standard care for HCV, blood samples (≤ 23.5 mL) may also be collected to obtain HCV viral load, liver enzyme levels,

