Diffusion-Weighted Imaging: DTI preprocessing will be performed using the DTI preprocess script (Takuya Hayashi, Center for Life Science Technologies, RIKEN, Kobe, JP) for FSL [(Smith et al., 2004) FMRIB, Oxford]. Scans will be corrected for eddy current distortion and motion. B_0 inhomogeneity distortion will be corrected using a B_0 field map (magnitude and phase) in FSL's fugue. DTI estimates (FA, λ_{1-3} , V_{1-3} , MD) will be calculated using DTIFIT. Voxelwise statistical analysis will be performed with TBSS (Smith et al., 2006) and nonlinear registration to the FMRIB58_FA common space will be conducted. Each subject's aligned FA data will be projected onto a mean skeleton. Voxelwise cross-subject statistics will be performed with FSL's *Randomise* with threshold-free cluster enhancement (TFCE).

Voxel-Based Morphometry: Structural images will be analyzed with FSL-VBM (Douaud et al., 2007) an optimized VBM protocol (Good et al., 2001) carried out with FSL (Smith et al., 2004). Images will be brain-extracted and tissue segmented, registered to the MNI-152 standard space using non-linear registration (Andersson et al., 2007), and flipped along the x-axis to create a left-right symmetric, study-specific gray matter template and modulated with a voxel-wise division by the Jacobian determinant of the non-linear transformation matrix to correct for local expansion or contraction. The modulated gray matter images will be smoothed with an isotropic Gaussian kernel with a sigma of 3 mm (FWHM = 7 mm). Group contrasts will be tested with FSL's *Randomise*, a permutation-based non-parametric procedure.

Statistical analyses and power. Statistical analyses for the project will be performed by the research team and the Biostatistics and Design Program at OHSU. All data sent to OHSU for statistical analysis will be coded.

Neuropsychiatric and laboratory measures. We plan to calculate the change in the response over six months between post- and pre-DAA therapy for each subject and use general linear models (GLMs) to assess whether average change differs among the four groups—either due to AUD, HCV, or the

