potential interaction of these factors—after possibly controlling for other subject-level covariates that remain constant (or nearly so) over the six months (e.g., age, sex, HCV genotype). Variables that could meaningfully vary over time (e.g., TFLB score, CIWA-Ar score) will be summarized in terms of a difference and then included as a covariate. Number of DAA therapy provider contacts will be included as an extra covariate that counts total contacts. All models will use “robust” (sandwich estimators) of variance to guard against potential misspecification of the underlying distribution of change scores or due to non-constant variance among the groups (Long and Ervin, 2000). The AUD \times HCV interaction will be assessed first in all models fit, and will be removed from the model only if evidence suggests ($p > 0.10$) these two factors don’t modify one another; otherwise, subsequent comparisons of each separate effect will be made within each level of the other (e.g., effect of HCV separately characterized for those with and then without AUD).

A supervised and directed approach will be taken in the exploratory analysis of inflammatory biomarkers. Principal component analysis (PCA) will be used to reduce the collection of ~12 correlated immune factors to a smaller number of uncorrelated linear combinations (the principal components) of biomarkers [e.g., (Bowman et al., 2012)]. Each component of this reduced set of uncorrelated patterns of inflammatory expression will be subjected to the same general linear models described earlier to determine whether AUD, HCV or AUD \times HCV are associated with it, even after adjustment for other covariates. If the overall test of association in the linear model shows significant ($p < 0.10$, for initial screen) variation among the groups, then separate models will be conducted on those biomarkers that most heavily contribute/dominate the principal component being screened. In this way, we may identify combinations of markers that are sensitive to AUD and HCV treatment outcomes, particularly CNS function.

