Power. We estimated group size using fmripower (Mumford and Nichols, 2008). The MATLAB-based program calculates a power estimate given the between-group and within-subject error terms associated with a two tailed t-test of regression coefficients. The results suggested that 30 subjects (male and female) per group would yield a power of 0.8 for the test comparison. This sample size yields an 80% chance for us to identify AUD \times HCV interaction effects of 0.91 standard deviation (SD) or larger at the 0.10 level of significance. Use of the higher alpha-level is done to lessen the chance of making a type II (overlook) error and mistakenly omitting this term from the model. We also have 80% power for a 0.05-level test to detect any main effect, for either AUD or for HCV, of at least 0.51 SD in size. **Table 2** shows the smallest average change (between post- and pre-DAA therapy) among groups that would be of practical interest and the subsequent main effects (AUD+ vs AUD-; HCV+ vs HCV-) and interactions that derive from these minimally relevant average changes. The anticipated SD for the change scores was derived from reported SDs of each outcome supported by literature, and then converted to a SD for the difference assuming a modest correlation of 0.60 between pre- and post-DAA responses within the same subject. The principal comparisons proposed in this work parallel those in our preliminary work, and we were able to readily demonstrate differences in planned comparisons between the groups. Therefore, the proposed 30 subjects per group should provide us with sufficient power to test the predictions, anticipating that a small number of participants with HCV may not achieve SVR (n = ~3-6).

Table 2. Statistical power to evaluate antiviral therapy outcomes of significant clinical impact

Response/outcome	SD(diff)	Treatment group ^a			Effects and Power ^b			
		AUD-/HCV-	AUD-/HCV+	AUD+/HC V-	AUD+/HCV+	AUD main	HCV main	Interact.
Cognitive performance^c								
Attention	2.25	3.5	3.7	1.2	3.5	-1.25 (0.85)	1.25 (0.85)	2.1 (0.81)
Memory	2.50	3.0	3.4	0.4	3.0	-1.50 (0.91)	1.50 (0.91)	2.2 (0.78)
Executive function	1.80	2.0	2.1	0.3	2.0	-0.90 (0.78)	0.90 (0.78)	1.6 (0.78)
Behavioral response								
Impulsivity (BART/MID) ^d	1.35	0	-0.2	-0.1	-1.5	-0.70 (0.80)	-0.80 (0.90)	-1.20 (0.78)
Alcohol use (TLFB)	18.9	0	-1.0	-18	-36	-26.5 (0.99)	-9.50 (0.78)	-17.0 (0.79)
Mental health								
Depression (BDI)	4.0	0	-3.5	-2.7	-11.0	-5.1 (0.99)	-5.9 (0.99)	-4.8 (0.94)

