received but not reviewed the letter, the researcher may ask if they are interested in hearing more about the study or receiving more information. After answering their questions, the researcher will schedule an Initial Study Visit for those who state they are interested in participating. If the Veteran has not received the letter, the researcher will only ask permission to send a second letter and confirm the individual's address; no other information will be requested at that time.

An appointment confirmation letter will be mailed to a participant after they have scheduled their initial visit. An appointment confirmation letter will also be sent prior to the week 24 visit. If a participant is enrolled in the study and not returning phone calls to schedule additional research visits, a no-show letter will be sent in the mail asking the participant to contact the research coordinator to discuss their interest in their continued involvement in the research study. If the research coordinator does not hear back from the participant within two weeks of sending the letter, the participant will be disenrolled from the research study.

Reminder phone calls will be made the day prior to scheduled on-site appointments. During reminder calls, study team will ask participants if they have recently had any recent exposure and/or symptoms of COVID-19. If a participant suggests that they might be experiencing symptoms or have had a known exposure to COVID-19, we will offer information on COVID-19 testing and self-isolation and postpone the study visit for at least two weeks following exposure or until symptoms are completely resolved. When the participant arrives for their appointment, their temperature will be taken using a digital thermometer and the same screening questions will be asked again before beginning the appointment. The participant will be sent home with the same information on testing and self-isolation upon indication or disclosure of any symptoms or exposure to someone with confirmed or suspected COVID-19. Also during confirmation calls, participants will be informed that masks are required to be worn during their entire visit. If a subject does not have access to a mask, the study team will provide one. Subjects will be instructed on how to properly care for their masks if they need to remove them during the study visit.

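### The change-score GLM drops everyone without a 6-month visit and does not condition on baseline, so baseline-related drop-out that differs among groups biases the contrasts

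*Combined protocol and SAP*

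**What the plan says.** Under Statistical analyses and power (Neuropsychiatric and laboratory measures), the combined protocol and SAP defines the analysis variable: "We plan to calculate the change in the response over six months between post- and pre-DAA therapy for each subject". Mean change is compared among the four AUD-by-HCV groups. The outcome battery has two time points: "The protocol will be conducted twice for each participant (baseline and 12 weeks after DAA therapy completion".

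Fixed covariates are optional and given by example: "after possibly controlling for other subject-level covariates that remain constant (or nearly so) over the six months (e.g., age, sex, HCV genotype". The baseline value of the outcome is not among the examples. Drinking (TLFB) and withdrawal (CIWA-Ar) scores enter differently; each "will be summarized in terms of a difference and then included as a covariate". The Questionnaire battery schedules the TLFB more often than the outcomes: "to be administered in-person at pre- and post-DAA therapy study visits, as well as over the phone at weeks 12 and 18". Sandwich variances are meant to "guard against potential misspecification of the underlying distribution of change scores".

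On missing follow-up, the project timeline (Table 3) says only that drop-out will be reviewed and follow-up efforts stepped up. Under Subject Identification/Recruitment, when an enrolled participant does not return scheduling calls and then does not answer a no-show letter within two weeks, "the participant will be disenrolled from the research study". No imputation, likelihood method or sensitivity analysis is named. Study Population gives 120 enrolled, Table 3 aims for 120 completed, and Table 2 bases power on all 30 per group.

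**The concern.** With two visits, a change score needs both. A participant seen only at baseline contributes nothing to the planned model, and the baseline of those who stay is subtracted but not conditioned on. With a pre-post correlation below 1, people with severe baselines tend to improve more through regression to the mean. If such people are lost preferentially from one group, its completers show a different average change for reasons unrelated to AUD or HCV. Sandwich variances address standard errors and do not correct this.

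Differential loss is plausible here. Visits are stopped and rescheduled for high breath-alcohol or withdrawal scores, which gives drinkers more occasions to miss one. In the sponsor's own preliminary Study 1, the AUD group had worse depression and PTSD scores. The contrasts at risk are the ones that answer Aim 2.

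**Working it through.** **Inputs from the documents** (Power paragraph, Table 2): 30 per group; pre-post correlation 0.60; detectable main effect 0.51 SD at level 0.05 and interaction 0.91 SD at level 0.10, each with 80% power. **Assumed, because the documents are silent:** drop-out rates, odds ratios of loss per SD of baseline severity, equal SDs at the two visits, normality, and a drinking effect of 0.4 where used.

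**1. The plan's own power.** In units of SD(diff), the SD of the change score:
- Main effect: SE = √(1/60 + 1/60) = 0.1826. Power = Φ(0.51/0.1826 − 1.96) = Φ(0.83) = 0.798.
- Interaction: SE = √(4/30) = 0.365. Power = Φ(0.91/0.365 − 1.645) = Φ(0.85) = 0.802.

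Both stated figures reproduce, with no loss at all.

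**2. Bias in one group's mean change.** With visit SD = 1, SD(diff) = √(2 − 2 × 0.60) = 0.894, and the slope of change on baseline is 0.60 − 1 = −0.40. If completers' mean baseline severity lies d below that of everyone enrolled in the group, the bias is 0.40 × d / 0.894.
- 20% lost, odds ratio 2: d = 0.129, bias 0.058.
- 20% lost, odds ratio 3: d = 0.186, bias 0.083.
- Across 10–30% lost and odds ratios 1.5–3: bias 0.018 to 0.121.
- Worst case, the most severe fraction q all lost: d = φ(z_q)/(1 − q) = 0.195, 0.350, 0.497 for q = 10, 20, 30%; bias 0.087, 0.157, 0.222. The 20% figure is 0.157/0.51 = 31% of the detectable main effect.

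**3. Bias in the contrasts.** Simulation of 20,000 trials, 30 per group, true change zero. The two-visit likelihood model has free group-by-visit means and a pooled pre-post slope. Entries are in SD(diff); positive means less apparent improvement in AUD+ on a severity scale.

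| Assumed loss | Contrast | Change score | Two-visit likelihood |
|---|---|---|---|
| None (SE 0.184 for both) | AUD | 0.00 | 0.00 |
| 20%, same baseline relation in all groups (OR 2) | all three | 0.00 | 0.00 |
| Baseline-related in AUD+ (OR 2, 20%), 10% random elsewhere | AUD | 0.06 | 0.00 |
| Same, OR 3 (21%) | AUD | 0.085 | 0.00 |
| Baseline-related in AUD+/HCV+ only (OR 3) | interaction | 0.087 | 0.00 |
| Driven by drinking in AUD+ (OR 3); drinking not in model | AUD | −0.083 | −0.084 |
| Driven by the unseen 6-month value in AUD+ | AUD | −0.086 | −0.141 |
| Baseline-related in AUD+; pre-post slope 0.2 in AUD+, 0.8 elsewhere | AUD | 0.173 | 0.075 |

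The third and fourth rows are 0.06/0.51 = 12% and 0.085/0.51 = 17% of the detectable main effect.

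**4. Precision.** The variance of a group's mean change (visit SD = 1, n enrolled, m completing) is 0.8/m for change scores and 0.64/m + 0.16/n for the likelihood model. At 20% loss (n = 30, m = 24) these are 0.0333 and 0.0320, a 4% reduction. Power for 0.51 SD goes from 0.705 to 0.722.

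**5. Covariates.** A TLFB or CIWA-Ar difference is undefined without follow-up, so keeping it would delete drop-outs again. A time-fixed covariate entered only as a main effect in a two-visit model cancels from the visit-by-group contrast when data are complete. It must interact with visit to match the planned adjustment of change.

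**The case against.** The strongest reply is that the bias is conditional and modest. Nothing in the documents shows that loss differs by group. The disenrolment rule applies to all four groups alike and records non-response rather than causing it. The plan also works at retention, with phone contacts at weeks 12 and 18, payment for the follow-up visits, reminder calls and scheduled reviews of drop-out. Under moderate assumptions the bias is below half a standard error (0.085/0.184 = 0.46). The alternative model rests on its own untestable assumption and does worse in one of the scenarios above. All of this stands. It limits the size of the point but does not supply the missing-data method that the plan lacks.

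A reader might infer more than the documents support:
- *Any baseline-related drop-out biases the contrasts.* It does not; the second row of the table gives zero.
- *The plan ignores baseline.* The score subtracts it, and the covariate list is open, so baseline adjustment is unlisted rather than excluded.
- *A two-visit model also cures loss related to drinking.* It does so only if observed TLFB enters the model; otherwise the bias is unchanged (−0.084 against −0.083).
- *The bias imitates the hypothesised weaker benefit in AUD.* The sign depends on the mechanism, as the table shows. Table 2 itself projects larger falls in AUD+ for depression (−5.1) and fatigue (−0.5), where loss of severe cases would work against the projected effect.

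**Conclusion.** The point holds in conditional form. The planned analysis is complete-case by construction, names no method for missing follow-up, and is biased for the group contrasts when baseline-related loss differs among groups in amount or strength. With about 20% loss in AUD+ at odds ratios of 2 to 3 per SD and 10% random loss elsewhere, the AUD effect is off by about 0.06 to 0.09 SD(diff). If the most severe 20% of AUD+ were all lost and no such loss occurred elsewhere, it would be 0.16. With a common mechanism and similar baselines it is zero.

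These sizes rest on the plan's correlation of 0.60 and on assumed drop-out rates, odds ratios, equal visit SDs and normality. The 0.16 is a bound for 20% loss and should not be read as an expected value. The case for changing the plan is that a two-visit likelihood model gives the same unadjusted estimate and standard error on complete data and removes this particular bias. It is not a remedy for every kind of drop-out.

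**What to change.** Rewrite the main analysis of the neuropsychiatric and laboratory outcomes as follows.
- Fit both visits for all enrolled participants by likelihood, with visit × AUD × HCV and unconstrained group-by-visit means. Baseline means must not be forced equal in this non-randomised cohort: a true 0.5 SD baseline gap would bias the contrast by 0.40 × 0.5/0.894 = 0.22 SD(diff).
- Use an unstructured covariance, group-specific if the data allow, with robust variance. Robust variance does not protect the estimates from a wrong covariance once data are missing (last row of the table).
- Enter fixed covariates and the count of provider contacts with visit interactions.
- Replace the TLFB and CIWA-Ar differences with observed baseline or visit-level values, using the week 12 and 18 TLFB calls. State which, since adjusting for baseline drinking and for concurrent drinking answer different questions.
- Test the visit-by-factor terms.

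Keep the change-score GLM as a completer sensitivity analysis. Report drop-out by group and by baseline severity and drinking. Add a sensitivity analysis for data missing not at random.

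The cost is SAP wording and more model specification, with no new visits or measurements. The drawbacks are the missing-at-random assumption, possible worse performance than change scores when loss depends on the unseen 6-month value, and little recovered power (0.705 to 0.722 at 20% loss).
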